Phase 2, which has also been completed, included patients from Phase 1 as well as additional patients (total N = 31) and was a randomized, placebo-controlled study to evaluate the efficacy, safety, PK, and PD of the 2 higher doses edasalonexent (67 and 100 mg/kg/day) over 12 weeks. Both doses were safe and generally well tolerated. There were no dose-dependent safety findings and, as in Phase 1, the majority of AEs were mild in nature and the most common treatment-related AEs were gastrointestinal, primarily mild and transient diarrhea. There were no treatment-related SAEs, drug discontinuations, or dose reductions, nor were there any concerning trends in chemistry, hematology, coagulation, or adrenal function assessments. Edasalonexent plasma exposures were consistent with those observed in Phase 1. The 100 mg/kg/day dose level demonstrated numerical improvement versus placebo across multiple efficacy measures, though not statistically significant. The 67 mg/kg/day dose group had mixed efficacy results compared with both the 100 mg/kg/day dose group and placebo, which in each case were not statistically significant.

In the open-label extension, which is currently ongoing, all patients (including those who received placebo in Phase 2) were to receive open-label edasalonexent at dose levels of 67 or 100 mg/kg for up to 124 weeks. Based on results from Phase 2 and the recommendation of the Data Safety Monitoring Board (DSMB), all patients in the 67 mg/kg/day dose group were switched to the 100 mg/kg/day dose group (which was already ongoing at the time the Phase 2 results were analyzed).

In an interim analysis conducted with all data through December 31, 2017, patients on edasalonexent at 100 mg/kg/day over 60 weeks of treatment showed a slower decline in timed function test speeds (10-meter walk/run test [10MWT], 4-stair climb, and time to stand) and North Star Ambulatory Assessment (NSAA) when compared to declines in the prior off-treatment control period. In addition to the muscle function assessments, supportive changes in measures of muscle health were observed,

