## 7.3. Evaluation of Adverse Events/Serious Adverse Events

### 7.3.1. Relationship to Study Treatment

Assessment of the association between the AE and study drug exposure is important for regulatory reporting. For each AE/SAE, the Investigator will determine whether there is a reasonable possibility that the AE may have been caused by the study drug according to the following categories:

Not Related: The AE is clearly not related to study drug.

Unlikely Related: There is no evidence of a causal relationship between study drug and the AE; although such relationship cannot be ruled out.

Possibly Related: There is some evidence supporting the possibility of a causal relationship between study drug and the AE.

Related: There is strong evidence that there is a causal relationship between study drug and the AE.

A relationship to the investigational product must be given for each AE/SAE recorded, even if there is only limited information at the time. The Investigator may change his/her opinion of causality in light of follow-up information, amending the AE/SAE report accordingly.

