4.13.1. Adverse Events

Adverse events will be coded using the MedDRA dictionary and displayed in tables and listings using System/Organ/Class (SOC) and Preferred Term (PT).

Analyses of adverse events will be performed for those events that are considered TEAEs, where treatment emergent is defined as any adverse event with onset after the administration of study medication through the end of the study (Week 52 visit) or any event that was present at Baseline but worsened in intensity or was subsequently considered drug-related by the investigator through the end of the study.

If the start date of an AE is partially or completely missing, then the date will be compared as far as possible with the date of the randomization. The AE will be assumed to be treatment emergent if it cannot be definitively shown that the AE did not occur or worsen during the post-randomization period (worst case approach).

The following general rules will be used:

- If the start day is missing, but the start month and year are complete, an AE will only be excluded as being on-study if the start month/year is before the month/year of randomization or if the stop date is before randomization.
- If the start day and month are missing, but the start year is complete, an AE will only be excluded as being on-study if start year is before the year of randomization or if the stop date is before randomization.
- If the start date is completely missing, an AE will be considered on-study unless the stop date is before randomization.

TEAE summaries will include the number and percentage of patients in each treatment group and overall. Summaries will include patients with:

- Any TEAEs
- Treatment-related TEAEs (Related, Possibly related)
- Maximum Severity of TEAEs
- Serious TEAEs, including any events resulting in death
- Treatment-related serious TEAEs
- TEAEs (and treatment-related TEAEs) leading to discontinuation of study drug

TEAEs are summarized by patient incidence rates, therefore, in any tabulation, a patient contributes only once to the count for a given adverse event (SOC or preferred term). TEAEs will also be summarized by SOC, PT, and severity and by SOC, PT, and relatedness. The most severe occurrence of a TEAE, as well as the most extreme relationship of the TEAE to the study procedure or treatment, will be used in tabulations of severity and relatedness in cases of multiple occurrences of the same TEAE.

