Additionally, the prevalence of common treatment-related TEAEs will be summarized by treatment group and overall across the treatment period stratified into 4-week intervals. A common treatment-related TEAE is one which occurs in over 10% of the patients in either treatment group. The objective of this analysis is to determine the time course of the incidence of these TEAEs. The following are the 13 4-week intervals:

- 1) Baseline – Week 4 (i.e., Day 1 – Day 28)
- 2) Week 5 – Week 8 (i.e., Day 29 – Day 56)
- 3) Week 9 – Week 12 (i.e., Day 57 – Day 84)
- 4) Week 13 – Week 16 (i.e., Day 85 – Day 112)
- 5) Week 17 – Week 20 (i.e., Day 113 – Day 140)
- 6) Week 21 – Week 24 (i.e., Day 141 – Day 168)
- 7) Week 25 – Week 28 (i.e., Day 169 – Day 196)
- 8) Week 29 – Week 32 (i.e., Day 197 – Day 224)
- 9) Week 33 – Week 36 (i.e., Day 225 – Day 252)
- 10) Week 37 – Week 40 (i.e., Day 253 – Day 280)
- 11) Week 41 – Week 44 (i.e., Day 281 – Day 308)
- 12) Week 45 – Week 48 (i.e., Day 309 – Day 336)
- 13) Week 49 – Week 52 (i.e., Day 337 – Day 364)

For each interval, the percentage of patients with the treatment-related TEAE in the interval will be presented. For each interval, the denominator for the percentage will be the number of patients who were in the study for any part of that period (i.e., patients who discontinued from the study prior to the start of the interval will be excluded). For each related TEAE, a patient will be included in the numerator if any of the following criteria are met:

- The start date of the TEAE is in the interval
- The stop date of the TEAE is in the interval
- The start date of the TEAE is before the interval and the stop date is after the interval
- The start date of the TEAE is before the interval and TEAE is ongoing

Note: For this prevalence TEAE analysis, if the start day and/or month of the AE is missing, a value of 01 for the day and January for the month will be used. If the stop day and/or month of the AE is missing, December will be used for the month and the last day of the month will be used for the day.

All adverse events occurring on study will be listed in patient data listings.

By-patient listings also will be provided for the following: patient deaths; serious adverse events; and adverse events leading to discontinuation of study drug.

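### The one adverse-event table by time interval counts only events the investigator rates related, so it cannot separate a change in occurrence from a change in attribution

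*SAP*

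**What the plan says.** SAP 4.13.1 (Adverse Events) plans that "the prevalence of common treatment-related TEAEs will be summarized by treatment group and overall across the treatment period stratified into 4-week intervals". The intervals divide Day 1 to Day 364, and the section states the purpose: "The objective of this analysis is to determine the time course of the incidence of these TEAEs". The causality rating enters twice.

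- **Entry rule:** "A common treatment-related TEAE is one which occurs in over 10% of the patients in either treatment group".
- **Numerator:** "For each interval, the percentage of patients with the treatment-related TEAE in the interval will be presented".

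The same section shows which ratings count: "Treatment-related TEAEs (Related, Possibly related". Events rated Not Related or Unlikely Related therefore drop out.

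Protocol 7.3.1 gives the rating to the investigator, event by event: "the Investigator will determine whether there is a reasonable possibility that the AE may have been caused by the study drug". It is open to revision: "The Investigator may change his/her opinion of causality in light of follow-up information".

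The other TEAE summaries in SAP 4.13.1 include all-causality counts by arm, by system organ class and preferred term, and by severity and relatedness. They cover the whole study, with each patient counted once. Event dates appear in patient listings. Protocol 9.12.3 has no adverse-event table by interval.

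**The concern.** The quantity displayed is the product of two things: how often the event occurs, and how often investigators attribute it to study drug. A trend in either moves the curve, and the table gives no means of telling them apart. That fits poorly with a stated aim of describing time course.

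A change in attribution over a year is conceivable. Protocol 2.2 reports from the 12-week Phase 2 study that "the most common treatment-related AEs were gastrointestinal, primarily mild and transient diarrhea", and an investigator who has that picture in mind might judge a late episode differently from an early one. Protocol 7.5 requires symptoms consistent with COVID-19 to be recorded as adverse events, and Protocol Appendix 2 places the pandemic after every patient had completed Week 26. A competing explanation for symptoms was thus available only in later follow-up. Both are inferences about behaviour. Neither is documented.

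At stake is how far the table supports any statement about whether common events persist or fade. Safety comparisons are mainly qualitative (SAP 4.13), so readers will rely on the displayed pattern. No efficacy conclusion is affected.

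**Working it through.** **The plan's own figure.** The SAP lists 13 intervals ending at Day 364. 13 × 28 = 364 = 52 × 7, so the grid reproduces exactly.

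**Inputs from the documents.** About 126 patients randomised 2:1 (SAP 4.1), that is 84 on edasalonexent and 42 on placebo; entry threshold over 10% in either arm; numerator restricted to Related or Possibly related.

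**Assumed inputs (not in the documents).** True prevalence of a term flat at 20% on edasalonexent and 10% on placebo in every interval; a share rated related that is the same in both blinded arms and may change between early and late intervals.

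**Formula for short episodes that start and end within an interval.** Displayed prevalence = true prevalence × share rated related. For a share falling from 80% to 40%:

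- edasalonexent: 20% × 0.8 = 16%, then 20% × 0.4 = 8%
- placebo: 10% × 0.8 = 8%, then 10% × 0.4 = 4%
- difference: 8 points, then 4 points
- ratio: 16/8 = 2.0, then 8/4 = 2.0

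**Range over other assumed shares:**

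| Share rated related, early to late | Edasalonexent shown | Placebo shown | Difference (points) | Apparent change within arm |
|---|---|---|---|---|
| 90% to 90% | 18% to 18% | 9% to 9% | 9 to 9 | none |
| 90% to 60% | 18% to 12% | 9% to 6% | 9 to 6 | falls 33% |
| 80% to 40% | 16% to 8% | 8% to 4% | 8 to 4 | falls 50% |
| 90% to 30% | 18% to 6% | 9% to 3% | 9 to 3 | falls 67% |
| 50% to 80% | 10% to 16% | 5% to 8% | 5 to 8 | rises 60% |

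An all-causality table would show 20% and 10%, a difference of 10 points, in every interval of every row.

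**Ongoing events.** The SAP counts an event in each interval it touches, including when it began earlier and continues. Each event carries one rating. If a fraction f of late prevalence consists of events that began early and were rated at the early share, the late edasalonexent figure in the 80%-to-40% case is 20% × [0.8f + 0.4(1 − f)] = 8% + 8% × f. With f = 0 it is 8%, as in the table. With f = 1 it is 16%, and there is no false trend. The rows above are therefore the extreme for each assumed change in share.

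**Entry rule.** Over 10% means at least 9 of 84 or 5 of 42 patients with a related event. A term affecting 15% of edasalonexent patients passes on that arm only if more than 10/15 = 67% of them have it rated related; at 20%, more than 10/20 = 50%.

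**The case against.** The strongest objection is that the mechanism is assumed. Protocol 7.3.1 asks the same causality question throughout, and the Phase 2 summary in Protocol 2.2 is background, not guidance on rating. Knowing that gastrointestinal events are typical of the drug could just as well lead investigators to keep rating them possibly related in month 9. This stands: the documents do not show drift or its direction.

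Blinding should make any drift similar in the two arms, which preserves the relative comparison. This also stands, as the constant ratio of 2.0 shows. The within-arm trend and the absolute difference are not protected.

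Sampling noise is large. With 84 and 42 patients, the standard error of a 20% v 10% difference in one interval is √(0.2 × 0.8/84 + 0.1 × 0.9/42) = 6.4 points, more than the 4-point distortion in the main illustration. A reader might infer that randomisation makes the causality rating unnecessary. That goes too far: single-interval differences of this precision do not settle causality, and a related-only view is a defensible supplement.

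A reader might also infer that a late excess attributed to other causes would be hidden. It would still contribute to the whole-study all-causality tables by arm and to the dated listings. What would be missing is a tabulation of when it occurred.

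Two points of scope remain. Table shells are in a separate document (SAP section 8), so the statement that this is the only interval table applies to the protocol and SAP text. SAP 4.13.1 also has a rule taking the most extreme relationship when a TEAE recurs, but it is written for the severity and relatedness tabulations; the SAP does not say that it governs the interval table.

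**Conclusion.** The point holds as a limitation of design. The only interval analysis described filters both its entry rule and its numerator on the investigator's rating, so it cannot distinguish a change in occurrence from a change in attribution. Under the assumed inputs the apparent change within an arm ranges from a 67% fall to a 60% rise with true prevalence flat. It is zero if the share rated related is constant, and smaller when ongoing events make up much of the late prevalence.

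A reader might infer that a declining curve in this table would be an artefact, or that the plan is built to make events look transient. The documents support neither. They show no drift, an opposite drift would produce a false rise, and neither document plans a claim of transience from this table. All-causality events are reported for the whole study; only their time course is absent. The matter is minor and descriptive, and worth changing because the change is cheap.

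**What to change.** In SAP 4.13.1, define the 13-interval table by treatment group on all-causality TEAEs. Select preferred terms whose all-causality incidence exceeds 10% in either arm, and count every TEAE of those terms in each interval under the existing date rules, whatever its rating. Keep the related-only table as a second panel.

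The data are already collected and the program is the same with the relatedness filter removed. The cost is a few more rows, mostly common childhood illnesses.

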## **APPENDIX 2. POTENTIAL MODIFICATIONS TO THE SCHEDULE OF ASSESSMENTS DURING THE COVID-19 PANDEMIC**

At the time of the COVID-19 pandemic, all enrolled patients had completed at least Week 26 so the implementation of alternative means to complete study assessments is intended for Week 39 and Week 52 only.

If the Investigator is able to perform the scheduled visit without impact to the safety of the patients and their families because of the COVID-19 pandemic, the Investigator should perform study assessments on site according to [Appendix 1](#).

If the Investigator is unable or unwilling to perform the scheduled Week 52 visit within window without impact to the safety of the patients and their families because of the COVID-19 pandemic, the Investigator, along with the patient/caregiver may decide to conduct the visit out of window (but in no case should the projected target date be changed by more than 2 months).

The COVID-19 pandemic has impacted study sites variably, so individual situations at each site may impact the capabilities of sites to perform certain study assessments. The purpose of [Appendix 2](#) is to outline considerations for sites to perform study procedures either on site or remotely by using alternative approaches to collect study assessments. While some study assessments can be performed remotely, it is acknowledged that others are not feasible to be conducted remotely.

As the top priority is safety, assessing for AE and concomitant medications is the highest priority to continue, which will occur remotely at intervals specified in [Appendix 1](#). Based on the safety profile of edasalonexent to date, and consideration that all patients in this study have been on study drug for 6 months, other safety assessments, including physical examinations, chemistry and hematology labs and urinalysis can be deferred for six-month intervals if not feasible given the COVID-19 pandemic.

The next priority is study integrity, which requires continued administration of study drug and efficacy assessments. Drug dispensation can take place according to local site procedures, including secured, temperature-controlled shipments to the patients' homes. Study drug accountability can be assessed remotely as well.

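### The 4-week TEAE table in SAP 4.13.1 measures period prevalence, but its stated objective is the time course of incidence, and no planned summary counts onsets by interval

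*SAP*

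**What the plan says.** All of the table's rules stand in SAP 4.13.1.

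- **Label.** The text opens with "the prevalence of common treatment-related TEAEs will be summarized by treatment group and overall". Its note on partial dates repeats the label: "For this prevalence TEAE analysis, if the start day and/or month of the AE is missing".
- **Objective.** Between the two it says: "The objective of this analysis is to determine the time course of the incidence of these TEAEs".
- **Numerator.** A boy counts in an interval if his event starts in it or stops in it. He also counts under two further criteria: "The start date of the TEAE is before the interval and the stop date is after the interval", and "The start date of the TEAE is before the interval and TEAE is ongoing".
- **Denominator.** Everyone in the study for any part of the interval, including boys already affected.
- **Partial dates.** A missing stop month becomes December and a missing stop day the last of the month. A missing start month becomes January and a missing start day the first.
- **Range.** "The following are the 13 4-week intervals", of which the last is "Week 49 – Week 52 (i.e., Day 337 – Day 364".

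The other TEAE summaries in SAP 4.13.1 count each patient once over the whole study. TEAEs run to the Week 52 visit. SAP 5.2 schedules that visit 364 days after randomization, and SAP 4.2.9 gives it a window of 10 days either way. Protocol Appendix 2 allows it to move further during the pandemic: "but in no case should the projected target date be changed by more than 2 months".

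**The concern.** An incidence time course shows when events begin. The four numerator criteria show who is affected at any time in the interval, which is period prevalence. The two agree in the first interval. After that they differ by the boys whose events carry over.

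Protocol 2.2 describes the commonest adverse effects as gastrointestinal, mostly mild and transient. A reader of this trial will want to know whether such events cluster at the start of dosing or keep arising over 52 weeks. The planned table cannot answer that, because a slowly falling column may reflect slow resolution or continuing onset. If event durations differ between arms, arms with the same onset rate can also look different.

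A smaller gap lies at the end of the table. An onset after Day 364 but before a late Week 52 visit is a TEAE and falls in no interval.

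**Working it through.** The SAP gives no incidence or prevalence figure to reproduce, so the check applies its rules to assumed events.

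**Inputs from the documents.** 13 × 28 = 364 days. N = 126 at 2:1 gives 126 × 2/3 = 84 boys on edasalonexent. Dropout is about 20% (SAP 4.1). **Assumed:** event counts, onset patterns and durations.

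**1. Persistence without new events.** Suppose 17 of 84 boys have onset on Day 10 and there are no later onsets.
- Events never closed, no dropout: the table shows 17/84 = 20.2% in all 13 intervals. New onsets are 20.2%, then 0%.
- Events of 7 days: both counts give 20.2%, then 0%.
- Events never closed, and 17 event-free boys (about 20%) leave over the year, 16 of them before the last interval: the figure climbs from 20.2% to 17/(84 − 16) = 25.0%. The count stays at 17.

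In 2,000 random data sets with no onset after interval 1 and no dropout, the numerator never rose.

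**2. Constant onset.** With 2 new cases per interval, incidence is flat at 2/84 = 2.4%. The table climbs to a plateau of 8/84 = 9.5% if each event lasts 84 days, and to 26/84 = 31.0% if none resolves.

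For exponential durations with mean m days and no withdrawals, the ratio of the interval 13 figure to the incidence is 1 + (m/28)(1 − exp(−336/m)). If 30% of boys are ever affected, incidence is 30/13 = 2.31% per interval.

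| Duration | Ratio | Interval 13 figure | Boys in 84 (new onsets: 1.9) |
|---|---|---|---|
| fixed 7 days | 1 + 6/28 = 1.21 | 2.8% | 2.4 |
| mean 14 days | 1.50 | 3.5% | 2.9 |
| mean 30 days | 2.07 | 4.8% | 4.0 |

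A 7-day event spills over only if it starts in the last 6 days of its interval, hence the 6/28.

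**3. Early onset only.** With 30% affected and all onsets spread evenly over Days 1–28, the interval 2 figure is 30% × (m/28)(1 − exp(−28/m)). Each later interval multiplies by exp(−28/m). True incidence after interval 1 is 0%.
- m = 14: 13.0% in interval 2, 1.8% in interval 3.
- m = 30: 19.5% and 7.7%.

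**4. Partial stop dates.** Take a first dose on 1 March 2019 and a 7-day event from 10 March, with stop day and month missing. The stop becomes 31 December, which is Day 306. The event then counts in 11 intervals instead of 1.

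**5. End of table.** If dosing starts on the day of randomization, the Week 52 visit is due on Day 365.
- At +10 days it falls on Day 375, leaving 375 − 364 = 11 days uncovered.
- At +2 months (taken as 61 days) it falls on Day 426, leaving 62 days, or 62/426 = 14.6% of that boy's time.

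**The case against.** The best defence is that the table is what its label says. The SAP calls it prevalence twice and the numerator fits that name, so a reader who infers that the numerator is wrong goes too far. The fault is one objective sentence that does not match, together with the absence of any onset count. This part of the defence stands and fixes the scope of the point.

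Three other strong readings are tempting and unsupported.
- **That the figure rises with no new events.** Without new onsets or withdrawals it can only stay level or fall. It rises only with continuing onsets or when event-free boys leave.
- **That risk is overstated three- to five-fold.** The formula does give 3.1 and 5.0 at means of 60 and 120 days. Those durations are assumptions, and they sit badly with events described as mild and transient. Protocol 7.7 also has unresolved events reviewed at later visits, so events that are never closed should be uncommon.
- **That late events are lost.** The 13 intervals cover the nominal 52 weeks, and later onsets stay in the overall TEAE summaries and listings. The 14.6% describes one boy at the maximum delay.

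It can also be said that onset dates are listed and that arms are compared only qualitatively (SAP 4.13). Both are true and limit the consequence. A listing is not a summary, however, so the stated objective is still unmet.

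**Conclusion.** The point holds in limited form. The objective names incidence while the table delivers period prevalence, and nothing else planned in the SAP supplies onset by interval.

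The size rests on duration, which must be assumed. It is close to nil for events of about 7 days with complete dates. Under constant onset with 30% ever affected, it is about one extra boy in 84 in the last interval at a mean of 14 days and two at 30 days. Unclosed events, and stop dates carried to December, lengthen the persistence.

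The gap after Day 364 is real but minor and affects this table only. Severity is low: the table is descriptive and safety-only, and no efficacy inference depends on it.

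**What to change.** In SAP 4.13.1:

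1. Keep the table and reword its objective as the time course of prevalence.
2. Add, by arm and interval, the number and percentage of boys with a first onset of that TEAE in the interval. The denominator is the boys in the study at the start of the interval with no earlier onset of that event, so that numerator and denominator match. Base any statement about incidence over time on these columns. Events present at Baseline that worsened have no onset on treatment, and events with an imputed start month may land in the wrong interval or before first dose. Report both in a separate row or footnote.
3. Add a final row from Day 365 to the Week 52 visit, marked as having variable length and few boys, and so not comparable with the 28-day rows.

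The cost is some SAP wording, extra columns from dates already collected, and one row. The table becomes longer and the last-row denominator is small. Recurrences do not enter the first-onset columns, but they remain visible in the prevalence figures.

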### 5.2.5. Treatment Discontinuation

A patient's study treatment may be discontinued at any time at the patient's/parent/legal guardian's request or at the discretion of the Investigator, Medical Monitor or Sponsor. The following may be justifiable reasons for the Investigator, Medical Monitor or Sponsor to discontinue a patient from treatment:

- The patient experiences an intolerable or unacceptable AE
- The patient is unable to comply with the requirements of the protocol
- The patient participates in another investigational study without the written authorization of the Sponsor

Discontinuation of treatment does not imply withdrawal from the study.

Patients who discontinue treatment prematurely will be asked to complete the early termination visit prior to their last dose of study drug as noted in the SOA in [Appendix 1](#).

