### **7.7. Follow-up of Adverse Events/Serious Adverse Events**

All AEs/SAEs documented at a previous visit/contact that are designated as not recovered/not resolved or recovering/resolving will be reviewed by the Investigator at subsequent visits/contacts.

All AEs will be followed until the parameter returns to its Baseline status, resolution of AE, completion of the patient's participation, agreement is reached between the Investigator and Sponsor that the event no longer requires follow-up, or study termination, whichever occurs first. SAEs will be followed until resolution, the condition stabilizes, or the Investigator and Medical Monitor agree that follow-up is no longer necessary. Rules for AE/SAE follow-up apply to all patients, including those withdrawn prematurely to the extent allowed by the patient's consent. The Investigator will ensure that follow-up includes further investigations consistent with appropriate medical management and patient consent to elucidate the nature and/or causality of the AE/SAE.

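### SAP 4.13.1: boys who leave the study with an open related TEAE can be counted in the numerator of later intervals but not in the denominator, which overstates interval prevalence (minor)

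*SAP*

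**What the plan says.** SAP 4.13.1 sets out the table after the main TEAE summaries: "The following are the 13 4-week intervals", running from Day 1 to Day 364. It covers related events seen in more than 10% of either arm, and its declared aim is to show how these events behave over time.

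- Denominator: "the denominator for the percentage will be the number of patients who were in the study for any part of that period". The SAP adds that "patients who discontinued from the study prior to the start of the interval will be excluded".
- Numerator: "a patient will be included in the numerator if any of the following criteria are met". There are four criteria: the event starts in the interval, it stops in the interval, it spans the interval ("The start date of the TEAE is before the interval and the stop date is after the interval"), or "The start date of the TEAE is before the interval and TEAE is ongoing".
- Partial stop dates: a missing month becomes December and a missing day becomes the last of the month. No limit is set at the date the boy left the study.

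Protocol 7.7 governs how long events are followed: "All AEs will be followed until the parameter returns to its Baseline status, resolution of AE", or until one of several other end points, including the end of the boy's participation, whichever comes first. The same section applies the follow-up rules to boys withdrawn early, as far as consent allows. Protocol 3.3.3.2 asks that a boy withdrawn because of an AE be followed until it resolves or stabilises.

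**The concern.** A prevalence needs a numerator drawn from its own denominator. Here only the denominator has an in-study condition. A boy who has left can still satisfy the ongoing-event criterion, the spanning criterion, or the stop-in-interval criterion if his event closes after he has gone. A program written from the four criteria as listed would count him.

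Open events at exit are foreseeable. An event that stabilises without resolving, or that is lost to follow-up, may never receive a stop date, and Protocol 7.3.3 allows an outcome of not resolved. At stake is the reading of the late intervals. This table would show whether the gastrointestinal events, described in Protocol 2.2 as typically mild and transient, do fade over 52 weeks. Carrying forward events in boys no longer observed makes them look more persistent than the data show.

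**Working it through.** The documents give no interval prevalence, so there is no planned figure to reproduce. The check is on what the rule does.

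**Inputs from the documents.** About 126 patients randomised 2:1 (SAP 4.1), so N is about 84 on edasalonexent and 42 on placebo. Dropout from all causes is about 20% (SAP 4.1): 0.20 × 84 = 16.8, about 17, and 0.20 × 42 = 8.4, about 8.

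**Inputs that are assumed.** For a given interval:
- W = boys in the arm who left the study before it began;
- k = those among W whose related TEAE has no stop date, or one that falls in or after the interval;
- x = boys still in the study who have the event.

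None of these is in the documents. I take k from 0 to 4 and W from k to 17 on edasalonexent, with a true prevalence near 5%.

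**Formulas.**
- Rule as written: (x + k)/(N - W)
- Numerator limited to the denominator set: x/(N - W)
- Excess: k/(N - W), which is never negative

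**One boy, no other withdrawals.** Edasalonexent: 1/(84 - 1) = 1/83 = 1.2 points. Placebo: 1/(42 - 1) = 1/41 = 2.4 points. Each figure rises as W grows; with W = 17 on edasalonexent it is 1/67 = 1.5 points.

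**Examples for one late interval (counts assumed).**

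| Arm | W | k | x | As written | Limited to denominator | Excess (points) |
|---|---|---|---|---|---|---|
| Edasalonexent | 4 | 0 | 4 | 4/80 = 5.0% | 4/80 = 5.0% | 0 |
| Edasalonexent | 2 | 2 | 4 | 6/82 = 7.3% | 4/82 = 4.9% | 2/82 = 2.4 |
| Edasalonexent | 4 | 4 | 4 | 8/80 = 10.0% | 4/80 = 5.0% | 4/80 = 5.0 |
| Edasalonexent | 17 | 4 | 3 | 7/67 = 10.4% | 3/67 = 4.5% | 4/67 = 6.0 |
| Placebo | 1 | 1 | 2 | 3/41 = 7.3% | 2/41 = 4.9% | 1/41 = 2.4 |
| Placebo | 2 | 2 | 2 | 4/40 = 10.0% | 2/40 = 5.0% | 2/40 = 5.0 |

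Over k = 1 to 4 and W = k to 17, the edasalonexent excess runs from 1/83 = 1.2 to 4/67 = 6.0 points.

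**Duration.** A boy who leaves by Day 84 with an event that is never closed is counted in intervals 4 to 13, which is 10 intervals. If the event is later given a stop date, he is counted only up to the interval containing that date.

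**Between arms.** The excess depends on a proportion, not a count. Three such boys on edasalonexent (W = k = 3) give 3/81 = 3.7 points; two on placebo (W = k = 2) give 2/40 = 5.0 points. The arm with fewer such boys can be inflated more.

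**The case against.** The best defence is that a percentage of patients ordinarily takes its numerator from its denominator, so a careful programmer would apply the in-study restriction to both. That may well be the intent. But the SAP lists explicit numerator criteria without saying so, and nothing elsewhere in either document supplies the restriction.

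The defence is stronger on size. Protocol 2.2 and 2.3 report no treatment-related drug discontinuations in the earlier study, so k may be small or zero. The table is descriptive and carries no planned test. TEAEs leading to discontinuation of study drug are separately summarised and listed by patient, so a reader could cross-check the late intervals. This all stands and keeps the point minor.

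A reader might go further in three ways that the documents do not support.

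- *That every event leading to withdrawal stays open to Week 52.* Protocol 3.3.3.2 and 7.7 extend follow-up to withdrawn boys, so many such events should receive a stop date. The problem lasts only while an event is recorded as open.
- *That the arm with more AE withdrawals is inflated more.* What matters is the proportion who left the study with an open related event. Stopping drug is not enough: "Discontinuation of treatment does not imply withdrawal from the study" (Protocol 5.2.5), and a boy who stops drug but stays remains in the denominator.
- *That the denominator ought to be boys on drug.* This is a preference. The SAP's TEAE window runs through the Week 52 visit, and Protocol 7.1.3 keeps recording AEs after drug is stopped. An on-drug denominator with the numerator limited to it would drop boys whose related event persists off drug.

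**Conclusion.** The numerator and denominator are defined on different sets of boys, and read literally the rule does not give a true proportion. The error can only be upward, by k/(N - W) in each affected interval. On the stated N and allocation that is about 1.2 points for one boy on edasalonexent and 2.4 for one on placebo. It reaches 6.0 points on edasalonexent if four boys leave with open related events of the same kind and 17 of 84 have withdrawn. These counts are assumptions, and with k = 0 the table is correct as it stands. The arm with the larger proportion of study withdrawals with an open related event is inflated more; which arm that would be cannot be told from the documents. No efficacy analysis, main TEAE incidence table or decision rule depends on this. Severity: minor.

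**What to change.** Add to SAP 4.13.1, for this table only: a patient is counted in an interval's numerator only if he is in that interval's denominator, and any event that is ongoing, has a stop date after study exit, or has a partial stop date imputed past study exit is treated as ending on the study exit date. Keep the in-study denominator. The listings should still show the event as recorded.

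The cost is one sentence in the SAP and a date filter in the program. The exit and event dates are already collected, and no other output changes.
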